3.2.2 Secondary Study Endpoints

There are no additional secondary endpoints

3.2.3 Exploratory Endpoints

There are no exploratory endpoints

4 Study Enrollment and Withdrawal

Eligible patients include those indicated and scheduled for a BPTB ACL reconstruction. Patients will be identified from faculty surgeon case logs at the NYU Langone Health, Langone Orthopedic Hospital Sports Medicine Division.

4.1 Inclusion Criteria

In order to be eligible to participate in this study, an individual must meet all of the following criteria:

- Patients undergoing ACLR with BPTB autograft
- Skeletally mature (as defined by closed growth plates on plain radiograph)
- At least 18 years of age
- Willing and able to provide consent

4.2 Exclusion Criteria

An individual who meets any of the following criteria will be excluded from participation in this study:

CONFIDENTIAL

This material is the property of the NYU School of Medicine and Langone Medical Center. Do not disclose or use except as authorized in writing by the study sponsor

Interventional Template Version: 11 January 2019

- knee with intact ACL
- skeletally immature (as defined by open physis on plain radiograph)
- pregnant
- less than 18 years of age
- previous ACL repair or reconstruction
- unable to speak english or perform informed consent
- multiligamentous knee injury (two or more ligaments requiring surgical attention)
- varus or valgus malalignment greater than 3 degrees

4.3 Vulnerable Subjects

No vulnerable subjects will be included in this study.

4.4 Strategies for Recruitment and Retention

No additional recruitment or retention strategies will be implemented.

4.4.1 Use of DataCore/Epic Information for Recruitment Purposes

This study will utilize EPIC to identify subjects by viewing the operative schedule for the Department of Orthopedic Surgery Sports Medicine division. Surgeons will present the study information to eligible patients at a preoperative office visit, which will provide subjects sufficient time to ask questions about the study and make a decision whether they would like to participate prior to their surgery.

Commented [MR1]: Subjects should not be approached for study inclusion on the day of their surgery. Edit to indicate that subjects will be approached at a pre-operative visit.

4.5 Duration of Study Participation

Study participation will include the time of surgery to the final 1-year postoperative visit.

4.6 Total Number of Participants and Sites

Based on an effect size of 0.25 with 3 cohorts, a total of 159 patients are needed with 53 in each group. Assuming a 15% drop-out/lost to follow up rate, each group will enroll 60 patients for a total n of 180 subjects.

4.7 Participant Withdrawal or Termination

4.7.1 Reasons for Withdrawal or Termination

Participants are free to withdraw from participation in the study at any time upon request. An investigator may terminate participation in the study if:

- Any clinical adverse event (AE), laboratory abnormality, or other medical condition or situation occurs such that continued participation in the study would not be in the best interest of the participant

CONFIDENTIAL

This material is the property of the NYU School of Medicine and Langone Medical Center. Do not disclose or use except as authorized in writing by the study sponsor

- The participant meets an exclusion criterion (either newly developed or not previously recognized) that precludes further study participation

4.7.2 Handling of Participant Withdrawals or Termination

Patient visits will correspond to the standard of care postoperative visit schedule. Therefore, in the scenario that a patient withdraws from the study, they will still be seen and evaluated by the attending surgeon at regular intervals in accordance with their regular care. However, no additional data will be collected from subjects who withdraw from participating in this study.

5 Study Agent (Study drug, device, biologic, vaccine etc.) and/or Procedural Intervention

The study agents in this study include Calcium phosphate cement (Quickset, Arthrex, Naples, FL) and Demineralized bone matrix (Allosync DBM Putty, Arthrex, Naples, FL). The control group will receive autogenous bone graft to fill the bone void.

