5.2.1 Administration of Intervention

The use of the study agent will be done in-person, intraoperatively, by the surgeon. Nearing the end of the procedure, either autologous bone graft, DBM, or calcium phosphate cement will be used to fill in the site where the bone blocks were initially harvested (as part of the autograft). This intervention will only occur once, and will not be repeated.

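### Investigators may end participation after a one-time treatment, and the plan makes no provision to keep collecting data, so some patients with complications may be lost from the pain and safety comparisons

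*Combined protocol and SAP*

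**What the plan says.** Section 4.7.1 sets out two routes out of the study. A participant may leave on request at any time. Separately, an investigator may terminate participation on either of two grounds:

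- An adverse event, laboratory abnormality or other condition "occurs such that continued participation in the study would not be in the best interest of the participant".
- A late exclusion: "The participant meets an exclusion criterion (either newly developed or not previously recognized) that precludes further study participation".

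Section 4.7.2 is headed as covering both withdrawals and termination, but its text speaks only of a patient who withdraws. For that patient, "they will still be seen and evaluated by the attending surgeon at regular intervals in accordance with their regular care", and "no additional data will be collected from subjects who withdraw from participating in this study". No sentence says what is collected after an investigator ends participation.

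On the treatment itself, Section 5.2.1 says: "This intervention will only occur once, and will not be repeated". Section 6.1.2 says that everything listed in 6.1.1 apart from the questionnaires is standard care.

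Sections 9.3.2 and 9.3.3 remove from analysis anyone who completes fewer than 80% of follow-up visits. Section 9.2 lists the three groups but gives no rule for analysing all randomised patients. No missing-data method or sensitivity analysis is described.

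**The concern.** Rules for ending participation make sense for a treatment that can be stopped. Here nothing remains to be stopped once the operation is over. What ends is mainly the collection of questionnaires and the research recording of adverse events, in a patient who goes on attending the same clinic.

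The grounds for termination include events that can follow from the filler and can themselves affect pain. Section 1.2.1 lists infection and fracture among the possible adverse effects of both added fillers. The lead surgeon places the allocated filler (5.3.1), and the body of the document describes no masking, so whoever decides on termination may know the arm. The result would be a post-randomisation loss that can depend on both arm and outcome.

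Patella fracture and adverse events are secondary outcomes (2.2), and the halting rule in 7.4 counts adverse events. Lost recording would affect these as well as the pain scores. Scores never collected cannot be recovered at analysis, so relaxing the 80% rule alone would not solve the problem.

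**Working it through.** **1. The two routes compared.**

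| Route | Allowed by | Data afterwards |
|---|---|---|
| Participant withdraws | 4.7.1 | None collected (4.7.2, explicit) |
| Investigator terminates | 4.7.1 | Not stated; the 4.7.2 heading covers it, the text does not |

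No other section provides for collecting data after termination. Section 12.4 deals only with revoked authorisation: it keeps data already collected and asks for permission to obtain at least vital status.

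**2. Interaction with the 80% rule.** Section 9.3.4 lists six postoperative visits: 1 week, 4-6 weeks, 3, 6, 9 and 12 months. Since 0.80 × 6 = 4.8, at least 5 are needed.

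- Data stop after the 6-month visit, before the 9-month visit: at most 4/6 = 66.7%, so the patient is excluded.
- Data stop after a complete 9-month visit: 5/6 = 83.3%, so the patient is kept but has no 12-month score.

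This takes a completed visit to mean one with study data. If clinic attendance alone counts, a terminated patient could pass the rule and still have no scores.

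**3. The plan's own figure.** Section 9.4 gives effect size 0.25, three groups, alpha 0.05, power 0.80 and 159 evaluable patients (53 per group). Reading 0.25 as Cohen's f in a one-way ANOVA, λ = N × f² = 159 × 0.0625 = 9.94, and the noncentral F distribution gives power 0.805. The exact solution is N = 157.2, or 52.4 per group, which rounds up to 53. The figure reproduces, which supports that reading of the effect size.

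If one arm differs from the other two by d, the SD of the three means is d√2/3. Setting this equal to f gives d = 0.25 × 3/√2 = 0.53 SD.

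**4. Illustration only.** Suppose a share p of one arm is terminated and lost, none in the other arms, and those patients' pain is D SD worse than that of the rest of their arm. The full arm mean is m + pD and the observed mean is m, so the shift is p × D. Neither p nor D is in the documents. With 60 enrolled per arm, 5% is 3 patients and 10% is 6. Percentages in the table are of 0.53 SD.

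| p | D = 0.5 | D = 1 | D = 1.5 | D = 2 |
|---|---|---|---|---|
| 2% | 0.010 (2%) | 0.020 (4%) | 0.030 (6%) | 0.040 (8%) |
| 5% | 0.025 (5%) | 0.050 (9%) | 0.075 (14%) | 0.100 (19%) |
| 10% | 0.050 (9%) | 0.100 (19%) | 0.150 (28%) | 0.200 (38%) |

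Similar losses in all arms would largely cancel in the comparison.

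**The case against.** The strongest objection is textual. The sentence that stops data collection names subjects who withdraw, and stopping collection after a true withdrawal is ordinary practice. A reader might infer that the protocol orders collection to stop when an investigator terminates participation. It does not say so. This objection stands. It changes the description of the defect but not the need for repair: if the inference is wrong, the plan is silent on terminated patients.

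A reader might also infer that patients with complications leave the comparison as a class. The documents do not support that. Termination is discretionary and qualified by best interest, or by the exclusion precluding further participation. When the remaining study activity is a questionnaire, those conditions may seldom be met. Adverse events are recorded at every scheduled follow-up visit (6.3.3, 6.3.4), and complication rates are to be analysed and reported (9.3.3, 9.4), so the plan expects such patients to remain. Section 1.2.1 also describes the filler risks as rare. All of this stands, and it limits the point to patients whom an investigator actually terminates.

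A later reconstruction for graft failure might be read as a newly developed exclusion. That is strained, because the prior-reconstruction criterion in 4.2 is better read as history before enrolment; otherwise every participant would meet it after the index operation. Pregnancy is a clearer example of an exclusion that can develop later.

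Finally, removal from the analysis comes in part from the 80% rule, which is a separate matter. That is correct, but the missing scores are not created by that rule and would not be restored by dropping it.

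**Conclusion.** The point holds in limited form. The plan permits termination for reasons that can be related to arm and outcome, after a treatment that is already complete, and provides no route to further data. Some patients with complications may therefore be lost from the pain and safety comparisons.

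The size and direction of any bias cannot be derived. The illustrative 0.01 to 0.20 SD (2% to 38% of 0.53 SD) assumes that all losses fall in one arm and that those patients have worse pain. Its upper end needs 6 of 60 patients terminated in one arm and none elsewhere, with pain 2 SD worse. If terminations are rare, the effect is probably small. A reader might conclude that the arm with more complications will look better; that follows only under these assumptions. Clinical follow-up continues in any case, so what may be lost on the safety side is research recording and not patient care. The change is worth making because it is cheap and because data not collected at the time generally cannot be recovered.

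**What to change.** In Sections 4.7.1 and 4.7.2:

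- Separate a participant's withdrawal of consent from investigator-initiated termination, and state what is collected after each.
- State that an adverse event, re-operation or late-recognised exclusion does not by itself end data collection.
- Continue questionnaires and adverse-event recording to 12 months unless the participant withdraws consent for data.

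In Section 9, state that these patients are analysed in their randomised arm.

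None of this alters clinical decisions about the patient. The cost is revised protocol and consent wording and a little extra follow-up work. Visits already take place as standard care, and Section 6.1.1 already allows patients to be contacted by phone when the questionnaires cannot be obtained in clinic.

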5.1.1 Device Specific Considerations

Not applicable

5.2 Study Agent Accountability Procedures

The study agents are normally available (as part of standard of care) in the surgical suite. As per standard protocol, the study agents will be handled in a sterile manner, and the date of expiry will be checked and confirmed with the surgical staff prior to usage. If a product is opened but unused, it will be discarded.

5.2.1 Administration of Intervention

The use of the study agent will be done in-person, intraoperatively, by the surgeon. Nearing the end of the procedure, either autologous bone graft, DBM, or calcium phosphate cement will be used to fill in the site where the bone blocks were initially harvested (as part of the autograft). This intervention will only occur once, and will not be repeated.

5.2.2 Assessment of Subject Compliance with Study Intervention

N/A

5.3 Study Procedural Intervention(s) Description

The use of the study agent will be done intraoperatively, by the surgeon. Nearing the end of the procedure, either autologous bone graft, DBM, or calcium phosphate cement will be used to fill in the site where bone blocks were initially harvested from the patella and tibia (as part of the autograft).

5.3.1 Administration of Procedural Intervention

Administration of the study agent during the procedure will be completed by the lead surgeon. This is a one-time procedural intervention that will not be repeated.

Commented [DP2]: Should this be autologous or autogenous?

Ensure the cohorts and agents used in the study are consistent throughout the protocol.

Commented [EH3R2]: Autologous

Commented [DP4R2]: Based on the background (p.9) and description of each cohort, the cohort that doesn't receive an agent gets autogenous bone (e.g. Sections 2.1 and 3.1 P.11)

CONFIDENTIAL

This material is the property of the NYU School of Medicine and Langone Medical Center. Do not disclose or use except as authorized in writing by the study sponsor

Interventional Template Version: 11 January 2019

6 Study Procedures and Schedule

6.1 Study Procedures/Evaluations

6.1.1 Study Specific Procedures

- Medical history (i.e. mechanism of injury, acuity of injury, co-morbidities, smoking status) will be collected by the surgeon during the first office visit
- Physical exam (i.e. height, weight, range of motion, points of pain, ability to bear weight, and assessment of ligamentous laxity) will be performed during the first office visit
- Radiographic images (which may include an X-ray, computed tomography scan, and/or magnetic resonance imaging scan, may be obtain as part of standard of care, independent of this study, to confirm the presence of a torn ACL and search for any concomitant pathology)
- A discussion of if the results of any study specific procedures (e.g., radiographic or other imaging or laboratory evaluations) will be provided to participant.
- If the patient is eligible for the study (i.e. meets inclusion/exclusion criteria), he/she will be informed of the study, and asked if they would like to participate (if yes, consent will be obtained by the surgeon or a study member)
- Once consented, the following questionnaires will be administered: VAS, KOOS, KUJALA IKDC
- On day of surgery, surgeon will ensure patient is aware of their participation in the study, and will consent them for the procedure
- Intraoperatively, when appropriate, the surgeon will use the appropriate graft (autologous bone graft, DBM, or calcium phosphate) based on the group to which the patient was randomized
- The patient will return for post-operative visits at the following intervals: 1 week, 4-6 weeks, 3 months, 6 months, 9 months, and 12 months. During each post-operative visit, the patient will be asked to complete the same survey as completed preoperatively; if unable to obtain during the office visit, patients will be contact via phone within 2 weeks of the visit.

6.1.2 Standard of Care Study Procedures

All of the above practices, aside from administration of the questionnaires, are standard of care.

6.2 Laboratory Procedures/Evaluations

N/A

6.3 Study Schedule

6.3.1 Screening

Screening (Day -28 to -1):

- Obtain informed consent of potential participant verified by signature on written informed consent form and provide patient with key information sheet regarding the study.
- Review medical history to determine eligibility based on inclusion/exclusion criteria.
- Review medications history to determine eligibility based on inclusion/exclusion criteria.

6.3.2 Enrollment/Baseline

Enrollment/Baseline Visit (Visit 1, Day 0)

- This is defined as the day of operation
- Obtain informed consent of potential participant verified by signature on study informed consent form (if consent was not already obtained during a pre-surgical visit)

CONFIDENTIAL

This material is the property of the NYU School of Medicine and Langone Medical Center. Do not disclose or use except as authorized in writing by the study sponsor

Interventional Template Version: 11 January 2019

- Provide the patient with a key information sheet regarding the study (if consent was not already obtained during a pre-surgical visit)
- Verify inclusion/exclusion criteria.
- Obtain demographic information, medical history, medication history, alcohol and tobacco use history.
- Obtain preoperative questionnaire of primary and secondary outcomes (VAS, KOOS, KUJALA IKDC)
- Record vital signs, results of examinations, other assessments.
- Administer the study treatment intraoperatively (i.e. use of autologous bone graft, DBM, or calcium phosphate)

6.3.3 Intermediate Visits

6.3.3.1 Visit 2

Visit 2 (1 week \pm 4 days)

- Record adverse events as reported by participant or observed by investigator.
- Obtain questionnaire for primary and secondary outcomes (VAS, KOOS, KUJALA IKDC)

6.3.3.2 Visit 3

Visit 3 (4-6 week \pm 2 weeks)

- Record adverse events as reported by participant or observed by investigator.
- Obtain questionnaire for primary and secondary outcomes (VAS, KOOS, KUJALA IKDC)

6.3.3.3 Visit 4

Visit 4 (3 months \pm 3 weeks)

- Record adverse events as reported by participant or observed by investigator.
- Obtain questionnaire for primary and secondary outcomes (VAS, KOOS, KUJALA IKDC)

6.3.3.4 Visit 5

Visit 4 (6 months \pm 4 weeks)

- Record adverse events as reported by participant or observed by investigator.
- Obtain questionnaire for primary and secondary outcomes (VAS, KOOS, KUJALA IKDC)

6.3.3.5 Visit 6

Visit 4 (9 months \pm 4 weeks)

- Record adverse events as reported by participant or observed by investigator.
- Obtain questionnaire for primary and secondary outcomes (VAS, KOOS, KUJALA IKDC)

6.3.4 Final Study Visit

Final Study Visit (12 months \pm 4 weeks)

- Record adverse events as reported by participant or observed by investigator.
- Obtain questionnaire for primary and secondary outcomes (VAS, KOOS, KUJALA IKDC)

CONFIDENTIAL

This material is the property of the NYU School of Medicine and Langone Medical Center. Do not disclose or use except as authorized in writing by the study sponsor

6.3.5 Unscheduled Visit

In the event of an unscheduled visit, no questionnaire will be administered.

7 Assessment of Safety

7.1 Specification of Safety Parameters

7.1.1 Definition of Adverse Events (AE)

An **adverse event** (AE) is any symptom, sign, illness or experience that develops or worsens in severity during the course of the study. Intercurrent illnesses or injuries should be regarded as adverse events. Abnormal results of diagnostic procedures are considered to be adverse events if the abnormality:

- results in study withdrawal
- is associated with a serious adverse event
- is associated with clinical signs or symptoms
- leads to additional treatment or to further diagnostic tests
- is considered by the investigator to be of clinical significance

7.1.2 Definition of Serious Adverse Events (SAE)

Serious Adverse Event

Adverse events are classified as serious or non-serious. A **serious adverse event** is any AE that is:

- fatal
- life-threatening
- requires or prolongs hospital stay
- results in persistent or significant disability or incapacity
- a congenital anomaly or birth defect
- an important medical event

Important medical events are those that may not be immediately life threatening, but are clearly of major clinical significance. They may jeopardize the subject, and may require intervention to prevent one of the other serious outcomes noted above. For example, drug overdose or abuse, a seizure that did not result in in-patient hospitalization, or intensive treatment of bronchospasm in an emergency department would typically be considered serious.

All adverse events that do not meet any of the criteria for serious should be regarded as **non-serious adverse events**.

7.1.3 Definition of Unanticipated Problems (UP)

Unanticipated Problems Involving Risk to Subjects or Others

Any incident, experience, or outcome that meets all of the following criteria:

- Unexpected in nature, severity, or frequency (i.e. not described in study-related documents such as the IRB-approved protocol or consent form, the investigators brochure, etc.)

CONFIDENTIAL

This material is the property of the NYU School of Medicine and Langone Medical Center. Do not disclose or use except as authorized in writing by the study sponsor

- Related or possibly related to participation in the research (i.e. possibly related means there is a reasonable possibility that the incident experience, or outcome may have been caused by the procedures involved in the research)
- Suggests that the research places subjects or others at greater risk of harm (including physical, psychological, economic, or social harm).

7.2 Classification of an Adverse Event

7.2.1 Severity of Event

For AEs not included in the protocol defined grading system, the following guidelines will be used to describe severity.

- **Mild** – Events require minimal or no treatment and do not interfere with the participant's daily activities.
- **Moderate** – Events result in a low level of inconvenience or concern with the therapeutic measures. Moderate events may cause some interference with functioning.
- **Severe** – Events interrupt a participant's usual daily activity and may require systemic drug therapy or other treatment. Severe events are usually potentially life-threatening or incapacitating.

7.2.2 Relationship to Study Agent

The clinician's assessment of an AE's relationship to type of graft used (i.e. isolated autologous bone graft, DBM, calcium phosphate) is part of the documentation process, but it is not a factor in determining what is or is not reported in the study. If there is any doubt as to whether a clinical observation is an AE, the event should be reported. All AEs must have their relationship to study agent assessed. In a clinical trial, the study product must always be suspect. To help assess, the following guidelines are used.

- **Related** – The AE is known to occur with the study agent, there is a reasonable possibility that the study agent caused the AE, or there is a temporal relationship between the study agent and event. Reasonable possibility means that there is evidence to suggest a causal relationship between the study agent and the AE.
- **Not Related** – There is not a reasonable possibility that the administration of the study agent caused the event, there is no temporal relationship between the study agent and event onset, or an alternate etiology has been established.

